Due to states of emergency or pandemic situations, subject visits may be conducted via phone or video conference. PROs eligible for completion by interview at such visits are the IMPACT III and WPAI Questionnaires. In this situation, sites will read the PRO questions and response options to the subject and record the subject's responses. The subject's ability to view the PRO to understand the questions and response options should be preserved. Sites may share the questionnaire by videoconference or send the questionnaires (email or hard copy) to the subjects to allow them to read/understand the questions and responses when the subject is providing responses over the phone. The date and time of PRO data collection should be recorded along with who collected the information.

Subject Diary/Dosing Log

Subjects will be dispensed an electronic diary at Baseline and will be trained on how to complete the diary by site staff during the Baseline visit. All subjects should complete their subject diary on a daily basis throughout the entire study. The diary will be reviewed

by site personnel with the subject at each visit and collected at the Week 288/Premature Discontinuation Visit.

Non-Drug Materials provided to the Study Sites are described in Appendix H.

Subjects will also be trained on how to complete the dosing log by site staff. Dosing log must be recorded each time a dose is administered. In the dosing log, the date and time study drug administration, the kit number, vial/syringe number and the dose administered will be recorded. At every site visit, the site staff will record subject's body weight and will inform the subject or his/her caregivers about the amount/dose of study drug to be administered each week until the next site visit.

[figure not shown]
The dosing records will be reviewed and verified for compliance at each visit by the research personnel at the study center and reinforced if necessary. All relevant dosing information will be retained by the study coordinator and transcribed onto a drug accountability form at each visit. Additionally, any discernible departure from the protocol regarding study drug administration will be recorded on the source documents and in the appropriate drug accountability form.

The subject should bring the subject diary/dosing log to every study visit.

Study Drug Dispensing/Administration

Study drug will be administered to all subjects by the subject or their designated family member or friend under the supervision of site medical staff to reinforce proper aseptic subcutaneous injection technique. Subjects or a trained designated family member or friend or will perform the injections of the study medication in the subject's home during the weeks when a clinic visit is not scheduled.

At all office visits, subjects should be observed after study drug administration until judged medically appropriate by the study personnel. If an anaphylactic reaction or other serious allergic reaction occurs, administration of study medication should be discontinued immediately and appropriate therapy initiated. When dosing at home

subjects should be instructed to contact the site immediately with any signs or symptoms of a reaction.

[figure not shown]
Subjects should administer study medication on the same day of the week. The dosing dates for all doses of study drug should be calculated from the Baseline visit date. A \pm 3-day window is allowable for scheduled study dosing dates. For subjects that deviate from this dosing window, every effort should be made to bring the subject back to the original dosing schedule as soon as possible. For situations where bringing the subject back on the original dosing schedule will cause the dose to be out of the \pm 3-day window, please contact the AbbVie Medical Monitor for additional instructions.

Study drug kits will be assigned by the IRT. Since the amount of study drug that subject gets based on subject's body weight, at every site visit, study personnel will record subject's weight and will inform subject the amount/dose of study drug to be administered.

States of Emergency or Pandemic-Related Acceptable Protocol Modifications

Study drug may be shipped from the study site directly to the study subject's home if all the following criteria are met:

- Direct-to-patient (DTP) shipment of study drug is allowed by local regulations and the relevant ethics committee
- Study drug can be administered by the subject (or subject's caregiver) at home
- Subject agrees to have the study drug shipped directly to their home
 - Shipments may also include other study supplies (e.g., drug dosing diaries, paper copies of PROs). Instructions will be provided by AbbVie as to how a study site can initiate a DTP shipment using Marken, a global vendor selected by AbbVie to provide this service when necessary. Shipments of study drugs from the study site to a subject's home will be appropriately temperature controlled (qualified shipper or temperature monitoring) within the labeled storage conditions. Signature is required upon delivery; due to states of emergency or pandemic related social distancing, this may

be provided by the courier after delivery. Documentation of the shipment is to be retained by the clinical site.

 AbbVie will not receive subject identifying information related to these shipments, as the site will work directly with the courier.

The study site is responsible for meeting IRB/IEC reporting requirements related to DTP shipments of study drug, and for obtaining consent to provide delivery information to the courier and documenting this consent in source documents. AbbVie will submit any required notifications to the regulatory authority as applicable.

Body Weight Adjusted Volumes of Study Drug for Administration of Open Label Adalimumab 0.6 mg/kg Dosing (Weight Based) prior to Amendment 4 are described in Appendix F.

[figure not shown]
Subjects will be instructed to return all used and unused vials/syringes, Sharps containers and empty boxes at each visit for accountability.

Injections during subsequent study visits will be performed at the site by the subject or their designated family member or friend under the supervision of site medical staff to reinforce proper aseptic subcutaneous injection technique. Subjects or a trained designated family member or friend or will perform the injections of the study medication in the subject's home during the weeks when a clinic visit is not scheduled.

Endoscopy (Optional)

An endoscopy may be performed at the discretion of the investigator on the following occasions:

- Week 48
- Week 96
- Week 192
- Week 288/Premature Discontinuation

In this case, endoscopies may be either flexible sigmoidoscopy or colonoscopy.

Note:

• Biopsies to rule out malignancy, dysplasia, colon cancer or infection may be taken at the investigator's discretion.

The evaluation of endoscopies will be done by usage of the endoscopy subscore scale of the Mayo score and will include an assessment of friability.

[figure not shown]
5.3.2 Efficacy Variables

This study will utilize the PMS (and Mayo score if available) and PUCAI to determine efficacy of the study drug.

The following efficacy endpoints will be analyzed using summary statistics:

- The proportion of subjects who achieve clinical remission as measured by PMS (defined as a PMS ≤ 2 and no individual subscore ≥ 1) over time;
- The proportion of subjects who achieve clinical response as measured by PMS (defined as a decrease in PMS ≥ 2 points and ≥ 30% from Study M11-290 Baseline) over time;
- The proportion of subjects who achieve PUCAI remission (defined as < 10) over time;
- The proportion of subjects who achieve PUCAI response (defined as a decrease in PUCAI ≥ 20 points from Study M11-290 Baseline).

Efficacy will also be evaluated based on other measures of disease activity, including IMPACT III, WPAI, z-score for height and weight, bone age, BMI, and laboratory values as applicable. The proportion of subjects who achieve remission/response based on Mayo score and mucosal healing based on Mayo endoscopy subscore will be summarized for subjects with available Mayo score.

5.3.3 Safety Variables

Safety analyses will be performed on all subjects who receive at least one dose of study drug. Incidence of adverse events (AEs), changes in vital signs, physical examination results, and clinical laboratory data will be assessed.

5.3.4 Pharmacokinetic Variables

Pharmacokinetic and Immunogenicity:

[figure not shown]
Blood samples for serum adalimumab concentrations and immunogenicity status collected prior to Amendment 2 will be maintained for potential analysis of serum adalimumab and AAA concentrations. As appropriate, population pharmacokinetic analysis and/or any additional analyses may be performed.

Samples collected prior to Amendment 2 will be stored in a secure storage space with adequate measures to protect confidentiality. The samples may be retained for up to 5 years (where allowed by local guidelines) after completion of the study research. Samples that are not analyzed will be discarded by the end of the 5-year period specified above.

5.3.4.1 Cytokines and Serologic Variables

Samples collected prior to Amendment 2 may be analyzed for serologic antibodies and cytokines that may help predict disease behavior and help determine disease phenotypes or response to or tolerability of treatment. Some antibodies or immune markers insufficiently characterized or unknown may be understood to be important at the time of analysis. The samples may also be used for the development of diagnostic tests. The results of analyses will not be reported with the study summary.

Samples collected prior to Amendment 2 will be stored in a secure storage space with adequate measures to protect confidentiality. The samples may be retained for up to 5 years (where allowed by local guidelines) after completion of the study research.

Samples that are not analyzed will be discarded by the end of the 5-year period specified above.

[figure not shown]
5.4 Removal of Subjects from Therapy or Assessment

5.4.1 Discontinuation of Individual Subjects

A subject may withdraw from the study at any time. The Investigator may discontinue any subject's participation for any reason, including an adverse event, safety concerns or failure to comply with the protocol.

Subjects will be withdrawn from the study immediately if any one of the following occurs:

- Clinically significant abnormal laboratory result(s) or adverse event(s), as determined by the Investigator in consultation with the AbbVie Medical Monitor.
- The Investigator believes it is in the best interest of the subject.
- The subject requests withdrawal from the study.
- Inclusion and exclusion criteria violation was noted after the subject started study drug, when continuation of the study drug would place the subject at risk as determined by the AbbVie Medical Monitor (see Section 5.2 and Section 6.1.7).
- Introduction of prohibited medications or dosages when continuation of the study drug would place the subject at risk as determined by the AbbVie Medical Monitor.
- Subject is non-compliant with TB prophylaxis.
- The subject becomes pregnant while on study medication.
- Subject is diagnosed with a malignancy, except for localized non-melanoma skin cancer. Discontinuation for dysplasia or carcinoma in-situ of the cervix is at the discretion of the Investigator.
- Subject is diagnosed with lupus-like syndrome, multiple sclerosis or demyelinating disease.

• Subject is significantly non-compliant with study procedures which would put the subject at risk for continued participation in the trial, as determined by the Investigator, in consultation with the AbbVie Medical Monitor.

States of Emergency or Pandemic-Related Acceptable Protocol Modification

During states of emergency or pandemic situations, it has been necessary to employ mitigation strategies to enable the investigator to ensure subject safety and continuity of care. Acceptable mitigation strategies are identified throughout the protocol.

[figure not shown]
The investigator should contact the sponsor medical contact before discontinuing a subject from the study for a state of emergency or pandemic related reason to ensure all acceptable mitigation steps have been explored.

Interruption/Discontinuation of Study Drug Due to COVID-19 Infection

During the Study Drug Dosing Period, a subject with confirmed (viral test positive) or suspected COVID-19 infection can only be dosed with study drug if the following COVID-19 viral clearance criteria are met:

- Symptomatic subjects: At least 2 negative viral tests in a row, ≥ 24 hours apart after at least 10 days have passed since recovery, defined as resolution of fever without use of antipyretics and improvement in respiratory symptoms (e.g., cough, shortness of breath)
- Asymptomatic subjects: At least 2 negative viral tests in a row, ≥ 24 hours apart after at least 10 days have passed since prior positive result (note: subjects who develop symptoms will follow guidance above for symptomatic subjects)

Delays in study drug dosing due to the above COVID-19 testing guidance for subjects must be discussed with the AbbVie medical contact, along with the possibility of premature discontinuation from the study drug dosing period. Frequency or timing of COVID-19 testing and intervals between testing for the above viral clearance criteria may

be adjusted to account for epidemiologic trends, updated information regarding infectivity, and local/institutional guidelines.

If, during the course of study drug administration, the subject prematurely discontinues study drug use, the procedures outlined for the Termination Visit must be completed within 2 weeks of the last dose of study drug, and preferably prior to the initiation of another therapy. However, these procedures should not interfere with the initiation of any new treatments or therapeutic modalities that the Investigator feels are necessary to treat the subject's condition. Following discontinuation of the study drug, the subject will be treated in accordance with the Investigator's best clinical judgment.

[figure not shown]
A final phone call will be made to the subject at least 70 days after the last dose of study drug to determine the status of any ongoing AEs/SAEs or the occurrence of any new AEs/SAEs.

All attempts must be made to determine the date of the last dose of study drug and the primary reason for premature discontinuation. The information will be recorded on the appropriate eCRF page.

For subjects that are considered lost to follow-up, reasonable attempts must be made to obtain information on the final status of the subject. At a minimum, two phone calls must be made and one certified letter must be sent.

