The PUCAI score will be assessed using subject-reported symptoms and activity level. The answers should reflect symptoms and activity level during the previous 24 hours. The PUCAI scores of the last 2 days prior to each study visit will be averaged and used for the PUCAI scores for each study visit. The total PUCAI score will be rounded up to the next 5-point interval as applicable. In order to account for unavailable or excluded diary entries as per the provisions given below diary entries for the PUCAI score of the most recent 2 days within 10 days prior to each study visit will be used.

Diary entries of the following days should not be included in the 2 days prior to the visit that are evaluated for the PUCAI score: (1) the day the subject received medication for bowel preparation prior to endoscopy, (2) the day the subject underwent an endoscopy, and (3) 2 days following the endoscopy. Earlier diary entries will be used accordingly in order to provide the most recent data for 2 days prior to the respective study visit.

The subscore for the number of stools per 24 hours during days which a subject received anti-diarrheal medication will be scored as 15.

Mayo Score

All subjects will be provided with a Subject Diary at the Baseline Visit where they will record ulcerative colitis related symptoms. The Partial Mayo Score will be calculated from the subject diary at each visit beginning at Baseline. The average entry from the 5 days prior to each study visit will be used for each subject-reported subscore. In addition to the physical examination, the investigator should use the subject-reported

subscores of abdominal discomfort and functional assessment to determine the physician's global assessment subscore.

Normal number of bowel movement is the number of stools per day (24 hours) that is typical for the subject when having active UC but not experiencing a flare. Each subject serves as his or her own control to establish the degree of abnormality of the stool frequency.

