6.0 Analysis Conventions

General Considerations

All statistical analysis results will be reported using descriptive statistics. Descriptive summary statistics will be provided for the demographic and Baseline characteristics, efficacy, and safety parameters.

Continuous variables will be summarized by sample size (N), mean, standard deviation, minimum, Q1, median, Q3, and maximum. Frequency and percentages will be provided for the categorical variables. For dichotomized efficacy variables, data will be summarized by number and percent of subjects with 95% confidence interval.

Week 0 and Baseline Visit Date

Week 0 is defined as the Week 52 visit from the Study M11-290. This date is also referred to as the baseline visit date.

Definition of Baseline Measurement

Unless otherwise notes, the baseline value for a variable is defined as the last non-missing value before the baseline visit date (i.e., at or before the Week 52 visit from the Study M11-290). In some instances Study M11-290-Baseline will be used, but this will always be specified accordingly.

[figure not shown]
Definition of Final Measurement

Final evaluation during the study: the last non-missing observation collected in the study after the first dose of study drug.

Final evaluation during ADA exposure in Study M10-870 (for laboratory analyses): the last non-missing observation collected in the study within the ADA exposure window in Study M10-870 (see Section 9.1).

Definition of Rx Days (Days Relative to the First Dose of Study Drug)

Rx Days are calculated for each time point relative to the date of first dose of study drug in Study M10-870. They are defined as the number of days between the day of the first dose of study drug and the specific time point. Rx Days are negative values when the time point of interest is prior to the first study drug dose day. Rx Days are positive values when the time point of interest is after the first study drug dose day. The day of the first dose of study drug is defined as Rx Day 1, while the day prior to the first study drug dose is defined as Rx Day –1 (there is no Rx Day 0).

[figure not shown]

Definition of Analysis Windows

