All time points and corresponding time windows are defined based on Rx days. The protocol specified visits and corresponding time windows are presented in the table below. Measures will only be displayed at the visits where they were planned to be measured. For example, Mayo score is collected at Weeks 0, 48, 96, 192 and 288/Premature Discontinuation (dependent on availability of optional endoscopy data at these timepoints).

Assigned Visit	Nominal Day	Time Window (Rx Day Range)
Week 0	1	≤ 1
Week 4	29	2 to 43
Week 8	57	44 to 71
Week 12	85	71 to 127
Week 24	169	128 to 211
Week 36	253	212 to 295
Week 48	337	296 to 379
Week 60	421	380 to 463
Week 72	505	464 to 547
Week 84	589	548 to 631
Week 96	673	632 to 715
Week 108	757	716 to 799
Week 120	841	800 to 925
Week 144	1009	926 to 1093
Week 168	1177	1094 to 1261
Week 192	1345	1262 to 1429
Week 216	1513	1430 to 1597
Week 240	1681	1598 to 1765
Week 264	1849	1766 to 1933
Week 288	2017	1934 to 2101

If more than one assessment is included in a time window the assessment closest to the nominal day should be used. If there were more than one observation with equal distance to the nominal day the latest one will be used in analyses. For any given variable, if more

than one measurement exists for a subject on the same day, the average of the measurements will be considered to be that subject's measurement for that day.

Missing Data Handling

In general, missing Baseline and safety data will not be imputed.

Baseline Value is Missing:

Subjects will be excluded from analysis of change from Baseline if Baseline evaluation is missing.

Missing Efficacy and Outcome Evaluations:

The following methods will be used for imputing missing values to perform the efficacy analyses.

[figure not shown]
For interim analyses, missing values will only be imputed up to the timepoint a patient could have potentially reached at the data cutoff for analyses.

Observed Cases (OC): missing values will not be used for the observed case analysis.

Last Observation Carried Forward (LOCF): For categorical and continuous efficacy variables the following rules will be used for LOCF approach:

- Baseline and pre-baseline values will not be used to impute the missing post-baseline values, and
- Missing values after baseline will be imputed using the last non-missing values after baseline and prior to the missing value.

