10.1 General Considerations

No confirmatory testing for efficacy endpoints will be performed in this open-label study.

[figure not shown]
Endpoints that are of the binary type will be analyzed as proportions including 95% CIs. Endpoints that are of the continuous type will be analyzed as changes from baseline, and reported including 95% CIs. OC and LOCF (see Section 6.0) will be used, unless otherwise noted.

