10.4 Efficacy Sensitivity Analyses

Sensitivity analyses may be performed as deemed appropriate.

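### An exit score taken after another UC drug has started still counts as an adalimumab result in OC and LOCF; one named supportive analysis would deal with it (low severity)

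*Protocol*

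**What the plan says.** Protocol 5.4.1 states that, after premature discontinuation, the Termination Visit procedures "must be completed within 2 weeks of the last dose of study drug, and preferably prior to the initiation of another therapy". It adds that "these procedures should not interfere with the initiation of any new treatments or therapeutic modalities" the investigator considers necessary, and leaves later treatment to clinical judgment. Protocol Table 1 schedules PMS and PUCAI at the Week 288/Premature Discontinuation visit, with Mayo if the optional endoscopy is done.

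SAP 5.1 uses one Full Analysis Set for every analysis. SAP 6.0 assigns assessments to visits by Rx day. Its general definition reads: "Final evaluation during the study: the last non-missing observation collected in the study after the first dose of study drug". For LOCF it says: "Missing values after baseline will be imputed using the last non-missing values after baseline and prior to the missing value". OC leaves out missing values only. SAP 10.1 adds: "OC and LOCF (see Section 6.0) will be used, unless otherwise noted". SAP 10.4 says only: "Sensitivity analyses may be performed as deemed appropriate".

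Protocol 8.1.4 differs on missing data. By visit it plans observed data and non-responder imputation (NRI), with LOCF as one further summary at the last visit. In the SAP, NRI appears only in the abbreviation list.

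**The concern.** The objective is maintenance of response on adalimumab. Protocol 5.1 and 5.5.1 direct that children whose disease stays uncontrolled on the top dose be withdrawn. These are the children most likely to need another drug at once, and the protocol rightly refuses to delay it for a study visit. The exit score may then reflect the replacement.

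If the replacement turns a failing child into a responder or remitter by the visit, and that score is the one selected for its window, the child counts as an adalimumab success there. LOCF repeats the result. The error can favour adalimumab only. The proportions also feed an Interim Clinical Study Report for regulatory submission (Protocol 8.1.7, SAP 4.4), so it should be fixed in advance what each one measures.

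**Working it through.** The plan states no figure on this point, so there is nothing to reproduce. The check is of the text, followed by arithmetic on size.

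**1. Does any rule catch the score?**
- OC: no. The score is not missing.
- LOCF: no. It carries any post-baseline value forward.
- The protocol's NRI: not at the exit visit, because NRI fills missing data only.
- Medication-based scoring: the only such rule covers anti-diarrheal days (Protocol 5.3.1.1, Appendix D).
- SAP 10.4: no analysis is named.

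**2. Can the score move within two weeks?** For PUCAI, "The PUCAI scores of the last 2 days prior to each study visit will be averaged". The stool frequency and rectal bleeding subscores of PMS average 5 days (Appendix D). With a complete diary and the visit on day v after the last dose, PUCAI uses days v−2 to v−1 and the two PMS diary subscores use days v−5 to v−1. The latest start that puts every diary day on the new drug is:

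| Visit day v | PUCAI (v−2) | PMS diary subscores (v−5) |
|---|---|---|
| 14 | day 12 | day 9 |
| 7 | day 5 | day 2 |

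Missing or excluded diary days push the look-back earlier and weaken the effect. These limits do not apply to the Physician's Global Assessment (PGA), which also uses physical findings and performance status, or to the endoscopy subscore. PMS and Mayo can therefore move even if every diary day predates the new drug.

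**3. Size per child whose status changes (1/n).**
- LOCF, n = 55 (expected ex-Japan number, SAP 4.3): 1/55 = 1.8 points.
- OC, assumed n = 40, 30 or 20 observed: 2.5, 3.3 or 5.0 points.
- Lower bound: 0. Response is measured against Study M11-290 Baseline, so a child who would be a responder anyway adds nothing to the response rate.

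For scale, at an assumed 33/55 (60.0%) the exact 95% CI is 45.9 to 73.0. One child lies well inside it.

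**4. Size overall (illustration only; all rates assumed).** Shift in the LOCF remission proportion = d × s × f, where d is the share discontinuing, s the share of those starting another UC therapy before the visit, and f the share of those whose status changes.
- d = 20%, s = 10%, f = 10%: 0.2 points (0.1 children).
- d = 35%, s = 25%, f = 30%: 2.6 points (1.4 children).
- d = s = f = 50%: 12.5 points (6.9 children).

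**5. Persistence under LOCF.** There are 19 scheduled post-baseline clinical visits. After an exit at Week 24, 48 or 96, at most 15, 13 or 9 remain to be filled. Under the protocol's by-visit NRI those later visits would be non-response whatever the exit score. The exit visit itself and the protocol's last-visit LOCF summary would still use it.

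**The case against.** The strongest reply is that the effect needs a chain of events: discontinuation, a new drug started before a visit that the protocol already steers ahead of it, improvement within two weeks, a change of status, and selection of that score in its window. The study is open-label and descriptive with no confirmatory test. Using all data whatever the treatment can be a legitimate choice, and SAP 10.4 leaves room for further analyses. All of this stands as a limit on size. It does not close the gap: the SAP does not say that it intends such a choice, and its rules as written give the wrong credit when the chain occurs.

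A reader might also infer more than the documents support:
- **That the SAP's exposure limit on final laboratory values shows the cure.** It does not. SAP 9.0 counts exposure to 14 days after the last dose, so an on-time Termination Visit falls inside it. Only the start date of the other drug separates the two cases.
- **That carry-forward over up to 15 visits is the harm of this gap.** It arises mainly from the SAP using LOCF without the protocol's NRI. The counts are also maxima, because interim imputation is capped (SAP 6.0) and the study may end early (Protocol 5.4.2).
- **That on-study rescue is a further main route.** Protocol 5.2.3.3 prohibits the drugs, Section 7.0 makes their use a reportable deviation, and the exception in 6.3 sits in infection and surgery text.
- **That any new UC therapy should count as failure.** Protocol 5.2.3.2 allows steroids, immunomodulators and 5-ASA to be started on study, so the same drug begun a day after the last dose should not be a failure. Nor should a child in remission who stops for an adverse event.

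**Conclusion.** The point holds in limited form. A protocol-compliant exit score can be measured on another UC drug, and the stated OC and LOCF rules then count it for adalimumab. The bias is upward: at most 1.8 points per affected child under LOCF at N = 55, more under OC at the smaller assumed denominators, and possibly zero in total. It rests on three assumptions that the documents cannot settle: how many children start another drug before the visit, how many improve in time, and how many change status. A few children at most is plausible. The 12.5-point figure multiplies three assumed rates of 50% and should not be read as an estimate. No error rate is involved. This is a cheap improvement of low severity.

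**What to change.** In SAP 10.4, name one supportive analysis of the binary efficacy endpoints.
- **Trigger:** the first dose, after the last study dose and before the Termination Visit, of a UC therapy prohibited on study by Protocol 5.2.3.3 (another biologic, tofacitinib, systemic cyclosporine, tacrolimus or mycophenolate mofetil, or an intravenous corticosteroid), given for UC.
- **Handling:** scores dated after that start are neither used nor carried forward. If the discontinuation was for lack of efficacy or flare, the child is a non-responder from then on. Otherwise the last score before the new therapy is carried forward.
- **Not triggered by:** steroids, immunomodulators or 5-ASA permitted on study, or a switch to commercial Humira (a completion category in SAP 8.0).
- **Reporting:** give the number of children affected and keep the planned OC and LOCF results alongside. If the number is zero, that alone answers the question.

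The data are already collected: medication dates and reason for use (Protocol 5.2.3.1), changes through the Premature Discontinuation visit (5.2.3.2), and the primary reason for discontinuation (5.4.1). SAP 7.3 already counts medications to 14 days after the last dose. Unclear reasons should be classified before database lock. The cost is one extra table and slightly less favourable rates in that table.
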